#### 7.1 Consent

Prospective participants will be asked to confirm whether they have read and understood the PIS and will be encouraged to ask questions and be provided enough opportunities to discuss before deciding to take part in the study. Patients will be free to discuss the study with friends and family before reaching their decision.

After confirming the patient's eligibility to take part, a qualified member of the research team, who has received training in obtaining informed consent, will obtain consent. Informed consent will be obtained prior to the participant undergoing procedures that are specifically for the purposes of SINATRA study and out-with standard routine care at the participating site. The participant will be able to refuse to participate in the study without giving any reasons and this will not affect their standard treatment in any way.

If verbal translation is needed, this will be provided via a hospital interpreter or an independent interpreter or telephone translation services that are used within the University Hospitals of Coventry and Warwickshire NHS Trust.

The consent procedure will be undertaken by a delegated member of the research team and will involve:

- Discussion between the potential participant and an authorised individual who is knowledgeable about the research and about the nature and objectives of the trial and possible risks associated with their participation.
- Presentation of written material (e.g., information leaflet and consent document which must be approved by the REC and be in compliance with GCP, local regulatory requirements and legal requirements)
- Opportunity for potential participants to ask questions.
- Assessment of capacity. For consent to be ethical and valid in law, participants must be capable of giving consent for themselves. A capable person will:
  - o understand the purpose and nature of the research
  - understand what the research involves, its benefits (or lack of benefits), risks and burdens
  - understand the alternatives to taking part
  - o be able to retain the information long enough to make an effective decision
  - o be able to make a free choice
  - be capable of making this particular decision at the time it needs to be made (though their capacity may fluctuate, and they may be capable of making some decisions but not others depending on their complexity)
  - where participants are capable of consenting for themselves but are particularly susceptible to coercion, it is important to explain how their interests will be protected

Patients who are determined to lack capacity will be excluded from recruitment to the SINATRA study.

Consent will be taken prior to the THz scan. Patients who are identified by the research team may be contacted prior to their scheduled appointment at the clinic to introduce them to the trial. Patients identified on the day of first review will be given appropriate time to decide whether to participate in the SINATRA study.

## 7.1.2 Payment

Patients who are recruited will be offered £10 travel and parking expenses to compensate for any extra time incurred for involvement in the trial.

#### 7.2 Baseline data

The following information will be collected as part of baseline data:

- Patient hospital ID number
- Unique study ID assigned to participant
- Demographics including : age, sex, ethnicity, height, weight, BMI
- Provisional clinical diagnosis
- Location of area to be scanned

## 7.3 Trial assessments

After patient recruitment, individuals will have a photo taken of the area of skin to be scanned before being scanned with the THz skinometer. A non-toxic Easi-Mark Surgical Skin Marker will be used to draw around the area to be scanned for image registration (both study arms) and to control the amount of skin product applied in the fixed area (study arm 1 only). This will be performed by a delegated research team member in an appropriate environment as per standard trust policy.

- A. **Study arm 1**: A minimum of 6 (most likely 7) readings of the THz skinometer ("scan") will be conducted after measuring the area of interest (AOI) and area of unaffected skin (control area measurement), at the following time points:
  - 1. Pre-application THz skinometer ("scans") of the AOI and area of unaffected skin, and the reference standard (volar forearm)

- 2. Post-application scan-I: participant will then be requested to apply emollient used regularly by them to the dry skin and control area, following which after 10 minutes another THz skinometer ("scans") will be conducted of the AOI and control area
- 3: Post-application scan-II: Repeat scans of AOI and control area will be conducted 10 minutes following the post-application scan-I

Further scans may be required if a clear image is not received upon the first attempt. At each time point each area will be scanned a maximum of 3 times to ensure a clear image is received.

Following the completion of the scans this will be the end of participation in the trial and the patient will continue the standard treatment pathway.

**Study arm 2**: A minimum of 2 (most likely 3) readings of the THz skinometer ("scan") will be conducted after measuring the AOI, area of unaffected skin (control area measurement) and the reference standard (volar forearm).

As with study arm 1; each area can be scanned up to 3 times to ensure a clear image is received. If a participant has multiple cancerous areas on their body the team will select the area most appropriate/feasible to scan. If they are unable to receive a good image, they will select another area instead.

This will be the end of participation in the trial and the patient will continue the standard treatment pathway. Histological diagnosis will be collected remotely using patient notes/medical records at a later date (typically 2-4 weeks after biopsy) by a delegated research team member.

## 7.4 End of study definition

The study will close after the final scan on the final participant.

## 8. STATISTICS AND DATA ANALYSIS

The summary of the study process from approaching a patient about the study to collecting their data at the study visit consists of the following steps

- 1. Step 1: During a clinic visit, a patient will be approached to check whether they are willing to be screened and enrol in the study. We will record the number of patients that are approached and how many are willing to enrol in the study.
- 2. Step 2: For each patient willing to enrol, a study visit will be scheduled. A record of whether a patient comes for a scheduled study visit will be kept.
- 3. Step 3: Eligibility will be assessed during the study visit.
- 4. Step 4: If a patient is eligible, they will be asked whether they are still willing to be part of the study, that is, whether they consent to be enrolled/recruited in the study.

The process will continue until at least 150 patients are recruited in the study; 50 for benign dry skin conditions group and 100 in the skin cancer group (we will aim for 50 basal cell carcinoma patients and 50 malignant melanoma patients).

Data collected in step 1 will be used to estimate the rate of willingness to enrol in the study. It will be computed as the proportion of approached patients who indicate they are willing to enrol in the study. A conservative estimate for the rate of willingness will combine information in steps 1 and 2, where patients who do not come for the study visit are considered not willing to enrol in the study. Eligibility rate, computed using data in step 3, will be proportion of eligible patients among those assessed for eligibility. Proportion of eligible patients that are recruited will give the recruitment rate. These rates will be computed for the three study groups (benign dry skin conditions, basal cell carcinoma and malignant melanoma) separately.

For all consenting eligible patients, during the study visit, outcomes will be taken for the affected (area of interest) and unaffected (control) parts of the skin. For each group, a paired t-test will be used to compare the means of outcomes (e.g. skin hydration) for affected and unaffected parts. The corresponding mean difference between affected and unaffected parts and 95% confidence interval (CI) will also be reported. For affected parts, using one way analysis of variance (ANOVA), we will test whether the means for the three groups are equal. Pairwise comparisons using independent t-tests will also be performed, with mean difference and 95% CI reported. We will also compare unaffected parts means for the three groups similarly.

Since this is a feasibility study, we will test all hypotheses at 10% significance level. Also, we will not adjust for multiplicity associated with testing multiple hypotheses. However, for it to be worthwhile conducting a future large study to test utility of THz, clear signals (large differences), estimated using mean differences and 95% CIs, will need to be observed in this feasibility study.

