#### 5. STUDY SETTING

The SINATRA study will be run within the Department of Dermatology, University Hospitals Coventry and Warwickshire NHS Trust.

Prospective participants will include UHCW staff members and patients suffering from dry skin conditions and known and suspected skin cancer. The patients will be recruited from scheduled Dermatology out-patient clinics including routine general Dermatology clinics (study arm 1: dry skin conditions), two week wait (2WW) urgent Dermatology clinics for suspected skin cancer, and joint clinics run between Dermatology and Plastic Surgery (study arm 2: known or suspected skin cancer). UHCW staff members will be recruited via posters which will be displayed within UHCW and circulated to all staff in internal news bulletins.

The patients will be identified screened and recruited by delegated research team member (Dermatologists, Plastic surgeons, Research Nurse), and scanned with the THz skinometer by non-clinical scientists (Physicists), within a designated clinical area. All non-clinical scientists will have honorary contracts at UHCW, be on the delegation log and have up to date GCP training.

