## 7. TRIAL PROCEDURES

#### 7.1 Recruitment

Prospective participants will be recruited from scheduled Dermatology out-patient clinics including routine general Dermatology clinics (dry skin conditions), two-week wait (2WW) urgent Dermatology clinics for suspected skin cancer, and joint clinics run between Dermatology and Plastic Surgery. Eligible UHCW NHS Trust employees will also be able to participate in the trial in arm 1 only.

Prospective participants who fulfil the inclusion criteria will be invited to participate in the SINATRA study following their consultation, either by a member of the clinical team or the clinical research team. Initial approach and consultation can happen either before a patients clinic visit or on the day of their visit if contact cannot be made beforehand. Patients will not be randomised as part of this pilot feasibility study.

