## 7.1.1 Patient identification and Screening

Prospective participants will be identified and screened by a member of their direct healthcare team at the time of clinical review or prior to clinical review from referral letters or photographs. As part of screening following data will be collected for all patients who are invited to be part of the study, including those who decline entry to the study:

- patient hospital ID number
- Basic demographical data

Considering the efforts in the Trust to reduce the number of non-urgent patient visits due to the ongoing pandemic. We will endeavor to contact prospective participants either by telephone or email before their scheduled visit to the dermatology clinic to introduce them to the trial. If they are interested in finding out more they will be referred to a member of the study team, who will explain the study and provide the patient with the PIS and invitation letter following which a delegated member of the research team will confirm their eligibility. If the research team cannot contact the patient before their clinic visit, then a delegated member of the research team can approach them on the day of their visit to first introduce them to the study and offer them an invitation letter and PIS. Following this consultation and after the patient has had a suitable amount of time to consider the trial, they can be invited to enter the study and consent can be taken. In addition study posters

placed around UHCW will inform prospective participants (patients & staff members) about the ongoing trial.

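### The recruitment procedures in Sections 5 and 7 do not generate the denominators on which Section 8 defines the primary feasibility rates

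*Protocol*

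**What the plan says.** Section 3.3 makes the numbers screened, eligible, recruited, withdrawn and retained, and willingness to take part, the primary outcome. Section 8 turns these into rates through four steps:

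- Step 1: "During a clinic visit, a patient will be approached to check whether they are willing to be screened and enrol in the study".
- Step 2: "For each patient willing to enrol, a study visit will be scheduled".
- "Step 3: Eligibility will be assessed during the study visit".
- Step 4: those found eligible are asked for consent.

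The willingness rate is the "proportion of approached patients who indicate they are willing to enrol in the study". A conservative version also counts those who miss the study visit as unwilling. The eligibility rate is taken among those assessed at step 3. For the last rate: "Proportion of eligible patients that are recruited will give the recruitment rate". Each rate is to be computed separately for the dry-skin, basal cell carcinoma and melanoma groups.

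The procedures describe other routes:

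- Section 7.1: "Prospective participants who fulfil the inclusion criteria will be invited to participate in the SINATRA study following their consultation".
- Section 7.1.1: the care team screens at or before clinical review, using referral letters or photographs. On the route with contact before the clinic visit, the research team confirms eligibility after the information sheet and invitation letter have been given. On record keeping: "As part of screening following data will be collected for all patients who are invited to be part of the study", decliners included.
- Schedules of events: eligibility and invitation share the Screening column, ahead of Visit 1, and the footnote allows screening and recruitment on the day of the clinic appointment.
- Section 5: "UHCW staff members will be recruited via posters which will be displayed within UHCW". Section 7.1 limits staff to arm 1.

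**The concern.** A feasibility rate means something only if the people in its denominator are identified and counted as the definition assumes. Section 8 assumes that people are approached before anyone looks at eligibility, then return for a visit at which eligibility is settled. The procedures mostly look at eligibility first, at least provisionally, and may have no separate visit. Four things follow.

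- The step 3 eligibility rate would describe a pre-filtered group.
- Recruited over eligible changes its meaning with the flow that the site follows. Section 8.1 adds to this, because it explains the 80% as acceptance among eligible patients without saying that they have already agreed once and attended.
- The conservative willingness estimate depends on a visit that same-day recruits do not have.
- Staff who answer a poster were never approached in a clinic, so the dry-skin willingness rate has no rule for them.

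Section 2.1 wants these data to inform a definitive trial. A planner who takes 80% as uptake among all eligible patients could be out by a factor of two in the plan's own expected scenario. Patients screened out before invitation cannot be added later if no one logged them.

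**Working it through.** **Inputs (Section 8.1):** 50 recruits per group; recruitment rate 80%; eligibility 20% or 50%; willingness 20%, 50% or 80%. The expected scenario is willingness 50%, eligibility 20%, recruitment 80%. Margin of error ME = 1.96 × √(rate × (1 − rate) / n).

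**1. Reproduce Table 1 in the Section 8 order (expected scenario).**
- Eligible: 50 / 0.80 = 62.5, rounded up to 63.
- Assessed for eligibility: 63 / 0.20 = 315.
- Approached: 315 / 0.50 = 630.
- ME: willingness 1.96 × √(0.5 × 0.5 / 630) = 3.9%; eligibility 1.96 × √(0.2 × 0.8 / 315) = 4.4%; recruitment 1.96 × √(0.8 × 0.2 / 63) = 9.9%.

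All six columns reproduce (1575, 630, 630, 252, 394 and 158 approached).

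**2. Put eligibility first, with the same rates.** This assumes that eligibility is independent of willingness. 630 screened × 0.20 = 126 eligible and approached; × 0.50 = 63 willing; × 0.80 = 50 recruited.

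| Rate | Section 8 order | Eligibility first |
|---|---|---|
| Eligibility, 20% | n = 315, ME 4.4% | n = 630, ME 3.1% |
| Willingness, 50% | n = 630, ME 3.9% | n = 126, ME 8.7% |
| Recruited / eligible | 50/63 = 80%, ME 9.9% | 50/126 = 40%, ME 8.6% |

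The number entering stays 630. What each n counts, and its precision, change.

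**3. Two meanings of recruited / eligible.** Among all eligible people the rate is willingness × recruitment: 0.5 × 0.8 = 40%, 0.2 × 0.8 = 16%, 0.8 × 0.8 = 64%. Among those already willing and attending it is 80% throughout.

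**4. Effect of pre-screening on the step 3 eligibility rate.** Let f be the share of ineligible patients removed before the approach (not in the protocol; assumed). The rate at step 3 is 0.20 / (0.20 + 0.80 × (1 − f)).
- f = 0: 20%.
- f = 0.5: 0.20 / 0.60 = 33%.
- f = 0.9: 0.20 / 0.28 = 71%.
- f = 1: 100%.

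**5. Poster-recruited staff, dry-skin group, expected scenario.** The protocol gives neither the staff share nor their eligibility. Assume 10% to 50% of the 50 recruits are staff, 20% to 80% of responders are eligible, and 80% of those consent. Count responders as approached and willing.
- Low end (5 staff, 80% eligible): 5 / 0.8 / 0.8 = 7.8 responders. The 45 patients need 45 / 0.08 = 562.5 approached, of whom 281.25 are willing. Willingness = (281.25 + 7.8) / (562.5 + 7.8) = 51%.
- High end (25 staff, 20% eligible): 25 / 0.8 / 0.2 = 156.25 responders. The 25 patients need 25 / 0.08 = 312.5 approached, of whom 156.25 are willing. Willingness = 312.5 / 468.75 = 67%.

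The clinic rate is 50% in both cases.

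**The case against.** Section 8 can be defended on several points, and much of the defence stands.

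- Its definitions fit together and give Table 1 without error. A reader might infer that the denominators are wrong in themselves. They are not; the fault is that the procedures do not deliver them.
- The procedures are mixed. On the pre-contact route, eligibility is confirmed after interest and the invitation letter, which is close to the Section 8 order, and Section 7 puts eligibility before consent, as Section 8 does. So it is too strong to say that the procedures always settle eligibility before invitation. The mixture still leaves no single flow to count on.
- A reader might take 40% as the true rate and 80% as biased. The 40% is the product of two rates that the plan already reports, under independence. It is a different quantity, not an error in the 80%.
- A reader might conclude that the number to approach is miscalculated. The steps multiply, so the entry total does not depend on their order.
- Section 7.1.1 does not say that counts of screened patients will be discarded, and Section 3.3 lists that number as an outcome. But the only screening data it specifies are for invited people, so nothing in the text secures the count.
- Read literally, step 1 covers only patients approached in clinic, which would leave staff out of the willingness rate. The plan does not say so, and Section 7.1.1 directs posters at patients too.
- Same-day recruits affect only the conservative willingness estimate, where they would count as having attended.

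Counting rules can be left to an analysis plan. Here, though, the protocol itself fixes both flows and says whose data are kept, and an analysis plan cannot restore people who were never logged.

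**Conclusion.** The concern holds as an unreconciled participant flow that affects the primary outcome. The size depends on the rate:

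- **Eligibility:** inflated to the extent that pre-screening works. The 33% to 100% range rests on assumed removal rates, and 100% needs a perfect pre-screen.
- **Recruitment:** one phrase with two readings, 80% or 40% in the expected scenario and 16% to 64% for the second reading across scenarios, given independence.
- **Precision:** the intermediate n and margins of error in Table 1 do not apply to an eligibility-first flow. Willingness loses precision and eligibility gains it.
- **Staff:** a gap in one group of three, mainly in the willingness rate. The shift to 51%–67% depends on an assumed staff share and eligibility, and 67% is the extreme.

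The documents do not support a general claim of upward bias in all the rates, or of an error in the total of 630.

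**What to change.** Use one participant flow in Sections 7 and 8, and state on it:

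1. Where provisional and confirmed eligibility sit, and how same-day recruits pass through step 2.
2. A log of everyone pre-screened, including those not invited, with the reason.
3. The denominator of each rate: eligibility among those pre-screened; uptake among all eligible people approached; and, separately, consent among those who attend and are eligible.
4. That poster respondents, staff or patients, are reported separately and left out of the willingness and uptake rates.
5. Table 1 with its n and margins of error recomputed on that flow.

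The cost is protocol wording and a fuller screening log. A lower uptake figure will stand beside the 80%. Leaving staff out also costs precision in the dry-skin group. If staff are 10% to 50% of its recruits, the eligible clinic patients behind the 80% fall from 63 to between 56 (45 / 0.8) and 31 (25 / 0.8), and the margin of error rises from 9.9% to between 10.5% and 14.0%.

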## 1.3 Study population

The SINATRA study will collect preliminary pilot data from participants in a two-arm feasibility observational study.

- One arm will consist of 100 patients with known or suspected skin cancer (skin cancer defined as: incompletely excised BCC with histologically proven radial margin involvement; biopsy proven BCC, or pigmented lesions suspicious of malignant melanoma). Images will be taken in the clinic prior to planned skin surgery and later compared to the formal histology results after the primary (melanoma) or residual (BCC) tumour has been removed.
- 2. The second arm will consist of 50 patients with benign dry skin conditions (eczema, psoriasis, skin grafts, scars etc.) and will compare the water content of their skin before and after application of a propriety emollients in common usage (e.g. E45®, Aveeno®, Doublebase®). This will add to the existing dataset that has been recorded from healthy non-patient volunteers (unpublished data, University of Warwick). This may help to guide patient-specific emollient selection in the future.

This will add to the knowledge base to define the appearance of skin cancers under THz skinometry. The spectroscopic findings will not influence the established management that will have been planned in conjunction with a Consultant Dermatologist or Plastic Surgeon and the patient.

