## 3.2 1. Secondary objectives

- To explore if Terahertz skinometry can quantify skin hydration and will show an increase in skin water content after application of an emollient in dry skin conditions.
- To explore if Terahertz skinometry can quantify skin hydration and may indicate the presence of residual basal cell carcinoma after primary excision, or the localised inflammation caused by melanoma skin cancer.

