## 3.4 Secondary endpoints/outcomes

**Physiological and clinical outcomes**: The secondary outcome is an objective difference in skin hydration between normal skin, benign skin conditions, skin containing residual basal cell carcinoma and skin containing malignant melanoma. The secondary research end point will be after the comparison of scan data with formal reported histological analysis as part of the standard skin cancer management pathway.

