## Study arm 2 - patients only:

- Aged 18 years and over
- Confirmed or suspected skin cancer (incompletely excised BCC with histologically proven radial margin involvement, biopsy proven BCC or pigmented lesions suspicious of malignant melanoma).
- Diagnosed with an incompletely excised basal cell carcinoma skin cancer (either radial margin involvement on primary excision or following diagnostic punch biopsy).

- Clinically suspicious pigmented skin lesion (suspected melanoma) with a plan for surgical biopsy
- Capacity to give informed consent

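### Section 8 pools incompletely excised and biopsy-only BCC and tests them against unaffected skin, so the fixed test cannot isolate residual BCC after excision, and no test there uses the histology

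*Protocol*

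**What the plan says.** **Target.** Protocol 3.2 asks whether terahertz skinometry "may indicate the presence of residual basal cell carcinoma after primary excision, or the localised inflammation caused by melanoma skin cancer". The outcome in 3.4 likewise names "skin containing residual basal cell carcinoma and skin containing malignant melanoma".

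**Who enters.** Section 1.3 defines the cancer arm as "incompletely excised BCC with histologically proven radial margin involvement; biopsy proven BCC, or pigmented lesions suspicious of malignant melanoma", and the arm 2 criteria in 6.1 repeat this list. A further criterion in 6.1 describes incompletely excised BCC as "either radial margin involvement on primary excision or following diagnostic punch biopsy". So the BCC group can hold patients whose tumour was excised with an involved margin and patients who have had only a biopsy.

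**Analysis.** Section 8 works with three groups: benign dry skin, BCC and melanoma. "For each group, a paired t-test will be used to compare the means of outcomes (e.g. skin hydration) for affected and unaffected parts". It then compares affected skin across the three groups by ANOVA and pairwise t-tests, and does the same for unaffected skin. All tests are at 10%. A future large study is made conditional on large mean differences, judged with 95% CIs.

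**Histology.** Section 3.4 states: "The secondary research end point will be after the comparison of scan data with formal reported histological analysis". Sections 1.3 and 1.4 also announce the comparison, and 7.3, 8.4 and 9.1 cover retrieval and linkage. No test in Section 8 uses the result.

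**The concern.** Residual BCC after primary excision is looked for at a site that has already been operated on. The control in 7.3 is unaffected skin. In a post-excision patient, area of interest minus control therefore contains whatever surgery and healing did to the skin, plus whatever residual tumour adds. The paired test sees only the sum. The protocol gives reason to expect the first part to matter: 1.2, 1.3 and 6.1 list scars among the benign dry skin conditions, and 1.6 cites a terahertz case report on scarred tissue.

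Pooling adds a second route to the same ambiguity. Biopsy-only BCCs still hold the primary tumour, so a difference in the pooled group could come entirely from them.

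The between-group tests do not resolve this. They set BCC against melanoma and against a benign arm that mixes eczema, psoriasis, grafts and scars. None compares with an excision site found free of tumour.

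At stake is the reading of the pilot. Section 8 rests the case for a larger study on these mean differences, and a large BCC difference could meet that condition while saying nothing about residual tumour.

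**Working it through.** **Inputs from the protocol:** 50 BCC patients (Summary, 8.1); 10% significance (8); standardised difference 0.5 and 80% power for 50 v 50 (8.1).

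**Assumed, because the protocol does not give them:** the post-excision share of the 50, the size of any scar shift, and the share of re-excisions with residual tumour.

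**1. The protocol's own figure.** Two-sample t, two-sided 10%, noncentrality d × √(n1·n2/(n1+n2)) = 0.5 × √25 = 2.5, df 98, critical value 1.661: power 79.9%. The stated 80% reproduces, and it shows that the 10% is two-sided.

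**2. The paired test when residual tumour adds nothing.** Let a fraction f of the 50 be post-excision with shift s (in SDs of the paired difference) and the rest have no effect. Treating the mixture as a single distribution, the standardised mean is

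d = f·s / √(1 + f(1−f)s²), noncentrality d × √50, df 49, critical value 1.677.

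For f = 0.5 and s = 0.5: d = 0.25 / √1.0625 = 0.243, noncentrality 1.715, rejection 52%.

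| Post-excision share f | s = 0.3 | s = 0.5 | s = 0.8 |
|---|---|---|---|
| 25% | 15% | 22% | 37% |
| 50% | 27% | 52% | 83% |
| 75% | 47% | 82% | 99% |
| 100% | 67% | 97% | >99% |

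**3. Signal from unexcised tumours only.** If biopsy-only sites differ from control by 0.5 SD and post-excision sites do not differ at all, the same formula applies with the shares reversed. Rejection is 82%, 52% and 22% with 25%, 50% and 75% post-excision.

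In every case in steps 2 and 3 the residual-tumour effect is zero.

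**4. The contrast that bears on the objective.** Among post-excision patients, compare area of interest minus control between residual tumour present and absent on re-excision. Same formula as step 1, d = 0.5, with d now in SDs of that site-minus-control difference:

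| Post-excision n | Split | Noncentrality | Power |
|---|---|---|---|
| 50 | 25 v 25 | 1.77 | 54% |
| 25 | 12 v 13 | 1.25 | 33% |
| 12 | 6 v 6 | 0.87 | 21% |

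Unequal splits are weaker: 15 v 35 gives 48% and 4 v 8 gives 20%. Section 8.1 presents the independent t-tests as the lowest-powered comparisons; its 80% does not carry over to this one.

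**The case against.** - **Histology comparison is already promised.** Sections 1.3, 1.4 and 3.4 commit to it, and a statistical analysis plan not shown here could supply the test. This stands in part: the data will exist, and nothing in Section 8 forbids using them. A reader might infer that the study as a whole cannot tell residual tumour from scar. The documents support that only for the tests that Section 8 fixes. What remains is that Section 8 has already chosen the group and the comparator, and neither matches 3.2.
- **The 97% is not the expected behaviour of the plan.** A reader might take it as the chance of a misleading result. It requires all 50 patients to be post-excision, a scar shift of 0.5 SD and no contribution from tumour in any of them. Yet every patient with an excised BCC enters with an involved margin, so the scenario is a hypothetical null. This stands, and the half-and-half case with its range is the fairer illustration.
- **A p-value below 0.10 does not launch the next study.** Section 8 asks for large differences. If large meant 0.8 SD (an assumption; no threshold is set), a true 0.5 SD shift would give an observed standardised difference that big about 3% of the time at n = 50 and 10% at n = 25. This answers the size, not the confounding: a truly large scar effect would still mislead.
- **The protocol itself groups these patients.** Section 6.1 puts punch-biopsied tumours under incompletely excised BCC, so the mismatch is partly one of wording. True, but 3.2 specifies the situation after primary excision. That the scanned site is a scar is inferred, since the objective does not use the word.
- **Residual-negative cases may be few**, because all excised entrants had involved margins. This stands and limits what the added contrast can show.

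**Conclusion.** The point holds for the analysis fixed in Section 8. The pooled BCC test against unaffected skin does not isolate residual tumour from the effect of earlier surgery or from a signal confined to unexcised tumours, and no test there uses the histology. With half the group post-excision and no residual-tumour effect, it would reject in about 52%, or 27% to 83% over scar shifts of 0.3 to 0.8 SD. All shares and effects in that figure are assumed.

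The 80% in 8.1 is correct for 50 v 50. It does not apply to residual present versus absent, where power at d = 0.5 is about 21% to 54% under equal or near-equal splits.

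The weight is moderate. Residual BCC is one half of one of two exploratory secondary objectives in a feasibility study, and the primary objective is untouched. It is worth correcting because the change costs almost nothing and the go-forward judgement rests on these differences.

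**What to change.** In Section 8:

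1. Report post-excision BCC and biopsy-only BCC separately, with the number in each.
2. In the post-excision subgroup, add an exploratory estimate with 95% CI of area of interest minus control, residual tumour present versus absent on re-excision histology, giving the number in each category.
3. State that the pooled affected-versus-unaffected difference will not be read as evidence of residual BCC.
4. In 8.1, state that the 80% power does not apply to the contrast in item 2, and that its precision depends on a split not yet known.

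The scans and histology are already planned, so no new patients or measurements are needed. The cost is small subgroups and wide intervals, and the contrast may prove uninformative if few re-excisions are tumour-free. An AUC, or locking the terahertz values before histology is linked, is not needed to repair this defect.
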